12.0 Data Management

Limited demographic and personal health history data will be collected during the phone screen in order to screen out participants with conditions that might confound the research or put them at risk for an adverse event. All screening data will be kept in a binder in the locked office in the Brain Stimulation Lab

IRB Number: «ID»

Date Approved «ApprovalDate»

as per the requirements of the IRB. Screening data collected from participants who do not qualify for the study will be securely destroyed.

Most of the data collected in this study are imaging data. These data will be collected from the 3T MRI scanner at [name]. All imaging data will be automatically transferred to and stored on a password-protected, encrypted secure server that limits data access to personnel directly involved with the study. The data will be analyzed using standard imaging analysis software packages such as FSL and SPM. Quantitative outcome data will be stored and locked in individual subject folders and kept in the Brain Stimulation Lab and stored on a secured digital redcap platform.

Power Calculation: Assuming a threshold of 0.05, 12 subjects are required to achieve 80% power at the single voxel level for typical fMRI BOLD activations in a tactile stimulation fMRI paradigm(42). Our primary fMRI findings in 17 individuals suggest that a n=20 within-subject design is appropriate to show taVNS functional changes in chronic stroke. In a recent review of published TST trials, it is suggested to provide 80% statistical power with a medium to large effect size (cohens d=0.8), changes in activity level would require at least 20 subjects in the treatment group and 20 subjects in the control group(43). With 20 participants in the treatment group, (10 per cell), we will be able to determine effect size in an open label pilot design. One of the primary goals of this project is to determine effect sizes for the planned follow-up grant proposal.

13.0 Provisions to Monitor the Data to Ensure the Safety of Subjects

There are three areas in which safeguards to protect subjects from undue risk require discussion. These include: (1) procedures used to obtain informed consent, (2) procedures used to ensure confidentiality of the subject data, and (3) procedures used to minimize possible risks associated with the laboratory procedures. Regarding informed consent, participants are fully advised on the research procedures to be used, the amount of time required of them, the possible risks and benefits of the procedures, their right to refuse participation in the study without prejudice, their right to terminate participation at any moment without prejudice, and the name and telephone number of the principal investigator. All subjects will be required to have capacity to consent. Regarding confidentiality, subjects are informed that the information they provide will be kept strictly confidential, with access limited to the research staff. Participation in the study will be treated as confidential, as will all records. The identity of subjects will be protected with alphanumeric codes. All data will be kept in locked file cabinets or on secure servers designed for use and access by Brain Stimulation Lab members only.

An independent Data Safety Monitoring Board (DSMB) will be formed to advise the study investigators. The DSMB will review and evaluate accumulated study data to ensure safety. They also will make recommendations concerning continuation, modification, or termination of any of the taVNS studies. It will be composed of [name], MUSC neurologist with expertise in transcranial direct current stimulation (tDCS); [name], MUSC associate professor and assistant provost with extensive VNS, TMS, and tDCS experience; [name], MUSC neurologist with expertise in VNS for epilepsy.

The DSMB will review all the data from AIM 1 and we will not proceed to AIM 2 without their approval. They will provide an interim safety analysis during AIM 2 (n=10 of the planned 20).

We do not anticipate any adverse events to occur in this study, however the experienced research team has a long-standing record of recording and reporting unanticipated adverse events to the IRB. We will report any adverse event within 48 hours to the IRB and to the DSMB.

15.0 Risks to Subjects

taVNS: taVNS is nothing more than transcutaneous electrical nerve stimulation (TENS) of the auricular branch of the vagus nerve that innervates the ear. Although this novel therapeutic modality is still in the development and optimization process, risks are a combination of those to be expected by both the peripheral TENS and implantable cervical VNS.

TENS devices are FDA approved for pain relief and are available over the counter. The main risks associated with TENS are electrical hazards that may result in user discomfort or injury. The unit used in these studies (Digitimer DS7AH) is a 510(k) cleared electrical stimulator that meets the rigorous electrical standards of the FDA. Skin irritation, redness, or inflammation may occur under the stimulating electrodes if TENS current is delivered for a prolonged period of time.

Implantable cervical VNS is FDA approved for the treatment of intractable epilepsy and treatment resistant depression. Cervical VNS has risks associated with the procedure of implanting the nerve, and the surgery. None of those apply here. taVNS does have some minimal risks that are due to the actual stimulation of the nerve within the neck such as skin irritation. taVNS also has associated risks that may arise from the direct brain effects stimulating the vagus nerve. These theoretical risks associated with neuromodulation of the parasympathetic nervous system would also be applicable in the administration of noninvasive taVNS. They are the following: reduction of heart rate, blood pressure, and vasovagal syncope.

Given the minimal risk both of these already FDA approved methods introduce, we suspect taVNS will be a very safe procedure. taVNS is not intended to be a therapy for currently existing conditions and all subjects will be healthy controls with no previous history of neurological disorders or trauma.

MRI:

MRI tests are non-invasive and painless. There are no known risks or side effects associated with conventional MRI procedures except to those people who have electrically, magnetically or mechanically activated implants (such as cardiac pacemakers) or to those who have clips on blood vessels in their brain. There are no known additional risks for interleaved taVNS-fMRI procedures. However, an MRI may cause you to feel claustrophobic (uncomfortable in a small space) or anxious from the noises made by the machine.

This MRI scan will be used to answer research questions, not to examine your brain medically. This MRI scan is not a substitute for one a doctor would order. It may not show problems that would be picked up by a medical MRI scan. Nevertheless, a clinical neurologist or neuroradiologist will read your scan. If we find an abnormality we will let you know and will advise you to follow this up with your doctors. If you wish a copy of your MRI scan we can provide it to you on a CD. The MRI scans will be stored on research

computers for 7 years and then they will be destroyed. It is not possible to access them after you complete the study so please get a copy of your MRI on a CD if you think you might want it in the future. Despite efforts to maintain subjects' anonymity and confidentiality, there is always some minimal risk of people other than the study investigators gaining access to your health information. Every effort will be made to ensure that your health information will be collected and stored in a manner that ensures the highest level of protection of confidentiality.

Task-Specific Training:

TST is a form of peripheral occupational therapy with proven efficacy by multi-center clinical trial. It has been widely used in the clinical practice by occupational therapist. It is a more intensive therapy than conventional occupational therapy. It may cause muscle fatigue or mild soreness as a result of exercise, it usually resolves within 12-24 hours.

Motor assessments:

The series of motor evaluation test takes about 60-75 minutes to be completed. Most of them are part of daily clinical assessment. It occasionally causes fatigue and but patient has the option to adjust his/her pace to complete the test

Overground and Treadmill Walking:

The physical activity involved with this study may contribute to temporary muscle soreness or fatigue. These are normal responses to exercise and generally disappear within 1-2 days. Rest periods will be incorporated into the testing and training procedures, but participants will also be allowed additional rest at any time they wish during testing. Assistance will be provided during activities of walking or transferring from one surface to another, including the use of a support harness during treadmill walking. Despite these safety measures, as with any walking activity, there is a risk that participants may lose balance, stumble, fall, and experience an injury. Heart rate and blood pressure will be monitored during testing. Vital signs will be monitored routinely (at least every five minutes of activity) to make sure participants do not have a poor response to activity.

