Cortical reorganization in the VNS group restored pathologically inactive circuits (**Figure 1**). These findings have led to large scale clinical trials (Microtransponder, 2012) exploring the use of VNS-paired rehabilitation to restore upper limb function and are early positive indications of using paired-therapy for rehabilitation. The ongoing invasive cervical clinical trial will report out results in early 2020.

[figure not shown]

Figure 2. taVNS activates the vagal afferent network when compared to sham auricular stimulation. Badran et al. 2018

[figure not shown]
Transcutaneous Auricular Vagus Nerve Stimulation (taVNS) is a Noninvasive Alternative: The auricular branch of the vagus nerve (ABVN) spans from the main bundle of the vagus nerve and innervates the human ear and is the target of a novel form of noninvasive vagus nerve stimulation known as transcutaneous auricular vagus nerve stimulation (taVNS). Modern taVNS was perhaps first described by Ventureyra in 2000[11], with several more recent studies using this novel form of neuromodulation[14, 16, 29-34]. [name] (PI) and the team at the MUSC Brain Stimulation Lab have pioneered several of the early studies demonstrating that taVNS activates the afferent (parasympathetic) vagal system by using cardiac effects as a reliable biomarker to determine optimal stimulation parameters. Following the optimization of the parameter space, [name] conducted a novel concurrent taVNS/fMRI study exploring the direct brain effects of taVNS which revealed activation of the vagal afferent network induced by stimulation of the ABVN[13] (Figure 2).

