Participants will receive taVNS stimulation to their left ear via electrodes attached to the anterior wall of the outer ear canal (25Hz, 500us pulse width, 200% PT). This will not be a therapeutic dose of stimulation, but rather a test of fit, comfort, and closed-loop functionality of the system in development.

We will analyze the EMG data and use it to determine optimal EMG thresholding levels for an automated sensing algorithm to be applied in Aim 2.

This experiment is not intended to provide any benefit to the participant. This serves for a system development and refinement study. All participants in this aim will be able to enroll into Aim 2

Specific Aim 2 – Determine target engagement and optimal taVNS dosing and effect size of taVNS-paired TST to improve upper limb motor recovery (n=20)

Screening

[figure not shown]
Prospective participants will be individuals who had a stroke > 6months prior to contact and must meet the following criteria to participate in this study: 18-80 years old with an ischemic or hemorrhagic stroke that occurred at least 6 months prior; completed conventional rehabilitation therapy at least one month prior; Unilateral limb weakness with Fugl Meyer-Upper Extremity Scale score less than or equal to 58 (out of 66)

For more information on tVNS screening please see the uploaded tVNS screening form. Written informed consent will be obtained from all participants prior to participation in the experimental paradigm.

Study Design

After successful validation of the closed-loop taVNS system is established, Aim 1 participants will be offered the ability to enroll into the Aim 2 & 3 studies of this proposal (n=20), an open-label pilot trial exploring the use of taVNS-paired vs unpaired motor rehabilitation. The primary goal is to determine safety, feasibility, and effect size of this paired therapy.

Participants enrolled in this study will receive upper limb motor rehabilitation (3days/week for 4 weeks. 1 hour/session) by a trained occupational therapist who is part of the college of health

IRB Number: «ID»
Date Approved «ApprovalDate»

professions rehabilitation CORE.

Neuroimaging (baseline and final)

All scanning will be performed on a 3T Siemens TIM Trio (Siemens, Erlangen, Germany). High-resolution T₁-weighted anatomical images will be acquired for each participant. Diffusion kurtosis imaging (DKI) or diffusion tensor imaging (DTI) scans will also be acquired for each participant.

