Multiple Interleaved taNS/fMRI scan will be carried out each visit using a gradient echo-based echo-planar imaging (EPI) scan sequence. Biphasic electrical pulses (Current = 200% perceptual threshold; Pulse width = 500µs; Frequency = 25Hz) generated by a Digitimer DS7AH (Digitimer Ltd, Hertfordshire, England) located just outside of the scanner room will be delivered to a special non-ferromagnetic Ag/AgCl clip electrode via a 7-m shielded copper cable. The cable will enter the scanner room through a wave guard. A 100kΩ resister will be placed in series to the stimulating electrode to prevent artificially induced currents from the MRI scanner interacting with the cable and the ear electrodes.

Interleaved taVNS/fMRI pulses will be delivered to the same left tragus or earlobe location as conducted in Aim 1. E-Prime 2 software (Psychological Software Tools, Inc.; Sharpsburg, PA) will be used to trigger a series of tVNS pulses in a block design every 10th TR for exactly 10 TRs (e.g. stimulate during TRs 10-20, 30-40, 50-60, 70-80, 90-100, 110-120) in the scan sequence. A total of 6 interleaved stimulation blocks will be delivered over 8-10 runs. The entire scanning sequence should last less than an hour.

Task-specific training (motor rehabilitation)

All participants enrolled in the pilot dosing trial will receive TST by a trained therapist in the **QBAR CORE**. TST will be administered 3 times per week for 4 weeks (12 total sessions). Each session will last 1 hour, and participants will be connected to EMG electrode arrays that will sense movements while the affected limb is trained in functional tasks like reaching forward to hold a glass and drinking from it, picking up and using objects, fine motor task and dexterity training. During TST, taVNS will be delivered in a movement-gated fashion.

Collected Measures :

MRI: Participants will attend 2, 1-hour fMRI scans (baseline & post-treatment 18) at the MUSC Center of Biomedical Imaging [name] (**Part of the NI Core**). During these neuroimaging sessions, we will collect high resolution T1 structural scans, fMRI BOLD during sequential finger-tapping task (thumb to fifth finger) both paretic and nonparetic hands, followed by the concurrent taVNS/fMRI paradigm (lesioned and contralesional ear targets) developed by [name] here at MUSC.

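### No heart-rate or blood-pressure measurement is described around any taVNS exposure, so asymptomatic falls, which the protocol itself names as theoretical risks, cannot be assessed

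*Protocol*

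**What the plan says.** **The risks.** Section 15.0 (taVNS) carries over to taVNS the effects of acting on the parasympathetic system: "These theoretical risks associated with neuromodulation of the parasympathetic nervous system would also be applicable in the administration of noninvasive taVNS". It then lists them: "They are the following: reduction of heart rate, blood pressure, and vasovagal syncope". These are not the only risks named. The same section mentions electrical hazard and discomfort from TENS-type devices, and also says "taVNS does have some minimal risks that are due to the actual stimulation of the nerve within the neck such as skin irritation".

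**The goal.** For Aim 2, section 10.0 states: "The primary goal is to determine safety, feasibility, and effect size of this paired therapy".

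**The exposures.** taVNS is given in three settings, all in section 10.0: the single Aim 1 visit, the interleaved taVNS/fMRI scans at baseline and after treatment, and the training sessions, where "During TST, taVNS will be delivered in a movement-gated fashion".

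**The monitoring.** Under the Overground and Treadmill Walking heading of section 15.0: "Heart rate and blood pressure will be monitored during testing". The next sentence gives frequency and purpose: "Vital signs will be monitored routinely (at least every five minutes of activity) to make sure participants do not have a poor response to activity". Blood pressure otherwise appears only in section 5.0, as a baseline exclusion for uncontrolled hypertension.

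**The oversight.** Under section 13.0, adverse events go to the IRB and the DSMB within 48 hours. The DSMB reviews all Aim 1 data before Aim 2 may begin, and makes an interim safety review at 10 of the planned 20 participants.

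**The concern.** The protocol says which cardiovascular effects stimulation might produce and makes safety part of the primary goal, but it places the relevant measurement where no stimulation is described. Where stimulation is given, no such measurement is described.

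A fall in heart rate or blood pressure that causes no symptoms leaves no trace unless someone takes a reading. If the protocol is followed as written, a report that no such change was seen would mean only that nobody looked. The DSMB would decide on the move to Aim 2, and later conduct its interim review, without those readings. An analysis plan cannot repair this, because readings not taken during a session cannot be recovered afterwards. The participants are chronic stroke patients, most of whose stimulation is given while they exercise the affected arm.

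**Working it through.** The protocol states no figure on this point, so there is none to reproduce. The check sets each setting in which taVNS is given beside the measurements described for it.

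| Setting | Source | taVNS given? | Heart rate or blood pressure described? |
|---|---|---|---|
| Aim 1 mock session | Section 10.0, Aim 1 | Yes, to test fit, comfort and function | No; EMG only |
| taVNS/fMRI scans | Section 10.0, Neuroimaging and Collected Measures | Yes | No; imaging only |
| TST sessions | Section 10.0, Task-specific training | Yes, movement-gated | No; EMG only |
| Weekly and follow-up clinical assessments | Section 10.0, Collected Measures | Not described | No; motor scales |
| Overground and treadmill walking | Sections 10.0 and 15.0 | Not described | Yes |
| Screening or baseline | Section 5.0 | No | Blood pressure, for eligibility |

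Three further places agree with this:

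- The schedule table at the end of section 10.0 has rows for MRI, clinical assessment, kinematics and actigraphy, and none for vital signs.
- Section 4.0 names motor scales and kinematics as endpoints, and no cardiovascular measure.
- Section 13.0 announces three areas of safeguards, the third being the reduction of risks from laboratory procedures. It goes on to consent, confidentiality, the DSMB and adverse-event reporting, and describes no measurement during stimulation.

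**Amount of exposure without described readings**

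- Aim 1: 5 participants x 1 visit = 5 visits.
- Scans: 20 participants x 2 = 40 visits.
- Training: 3 sessions per week x 4 weeks = 12 sessions per participant. If all 20 Aim 2 participants receive taVNS in training, 20 x 12 = 240 sessions. Section 10.0 contrasts paired with unpaired rehabilitation, and section 12.0 gives 10 per cell. If unpaired means no stimulation during training, the figure is 10 x 12 = 120 sessions.

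**What can be learned about each named effect**

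| Effect | Route to the DSMB as written |
|---|---|
| Vasovagal syncope | Adverse-event report |
| Fall in heart rate or blood pressure with symptoms | Adverse-event report, without a planned reading |
| Fall in heart rate or blood pressure without symptoms | None |

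**The case against.** **Overt events are covered.** Syncope is visible, and symptomatic bradycardia or hypotension would come to notice. Section 13.0 sends any adverse event to the IRB and the DSMB within 48 hours. A reader might infer that the safety goal cannot be answered for any of the three effects, or that the DSMB would see nothing cardiovascular. The document does not support either inference. This objection stands, and it limits the point to asymptomatic changes.

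**The risks are called theoretical and are not the whole list.** This also stands. Skin irritation and discomfort are named too, so the three effects should not be presented as the only taVNS risks.

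**The background does not predict harm.** Section 2.0 says earlier work showed vagal activation "by using cardiac effects as a reliable biomarker to determine optimal stimulation parameters". A reader might infer that the protocol expects a harmful cardiac effect here. It does not say so: the sentence describes how parameters were chosen in earlier studies. It does show that the investigators regard cardiac response to taVNS as measurable.

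**The walking text might reach the training sessions.** That paragraph opens by referring to physical activity in the study generally and allows rest in both testing and training. Its vital-signs sentence refers to activity without naming walking, so someone could read it as covering TST. The heading, and the restriction of the heart-rate and blood-pressure sentence to testing, make the walking-only reading the more natural one. The wider reading would still leave out stimulation in the scanner. The ambiguity is itself a reason to reconcile the text.

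**Readings could not be attributed to taVNS.** Aim 2 is open label, no sham training arm is described, and exercise changes heart rate and blood pressure. This stands as a limit on what the data could show, but detection and description do not depend on attribution.

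**Conclusion.** The point holds in a limited form. No heart-rate or blood-pressure measurement is described during or around any taVNS exposure, so asymptomatic falls cannot be assessed at the Aim 1 DSMB review, at the review at 10 participants, or at study end. Syncope and symptomatic events rest on adverse-event reporting alone. The gap spans 5 Aim 1 visits, 40 scan visits and 120 to 240 training sessions.

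No event rate or confidence limit is attached. A zero-event bound depends only on the number of participants and would apply to any event in a study of this size, so it would not measure this gap.

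The conclusion rests on two assumptions. First, the walking paragraph means what its heading says. Second, no monitoring is set out in material not seen: section numbers 11 and 14 do not appear in the text available, and the tVNS screening form that section 10.0 refers to is separate. The trial remains interpretable for its motor outcomes, and the defect is in one part of the safety goal.

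**What to change.** Reconcile the Aim 1 and Aim 2 procedures in section 10.0, the schedule table, and the taVNS and walking paragraphs of section 15.0:

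1. Extend the heart-rate and blood-pressure measurement already used in the walking tests to the Aim 1 visit, the TST sessions and the taVNS/fMRI visits. State in section 15.0 which sessions the monitoring covers.
2. Add a vital-signs row to the schedule table.
3. Provide the readings to the DSMB at its Aim 1 review and at the review at 10 participants.

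The exact timing of readings and any action limits are for the investigators and the DSMB to set.

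The cost is a protocol amendment and a few minutes per session, which must be fitted into the one-hour training visit and the scan visit. The amendment should also say that readings taken during TST reflect exercise and stimulation together, and will be reported descriptively and not as effects of taVNS.
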